***** Part 3: Multiple imputation for tipping point analysis *****
*****
```

/* Part 3a, Primary imputation method: for parameters with no missing data at baseline */;

* MI in patients who prematurely discontinued IMP before the endpoint using the endpoint data from its own group (retrieved dropouts);

```
proc sort data=ads;
  by treat ptid;
run;
```

```
proc mi data=ads out=disc_mi nimpute=2000 seed=97531;
  where discontinue = "Y";
  by treat;
  var value0 valuen;
  monotone regression (valuen = value0 );
  mnar adjust (valuen / shift=0.1 adjustobs=(treat='2')); *2 denotes test drug group of lower dose;
  adjust (valuen / shift=0.1 adjustobs=(treat='3')); *2 denotes test drug group of higher dose;
run;
```

Statistical Analysis Plan

Version: Final 3.0

Lexicon Pharmaceuticals Protocol No. EFC15166

Date of Issue: 21 November 2019

Covance Study ID: 000000155203

* MI in patients who stay on the IMP until the endpoint visit using the endpoint data from the placebo group (wash-out MI);

```
proc sort data=ads;
  by ptid;
run;
```

```
proc mi data=ads out=comp_mi nimpute=2000 seed=75319;
  where discontinue="N" and (treat=1 or (treat ne 1 and valuen =. )); *1 denotes placebo group;
  class treat strata1 strata2;
  var treat strata1 strata2 value0 valuen;
  monotone regression (valuen = strata1 strata2 value0 );
  mnar adjust (valuen / shift=0.1 adjustobs=(treat='2')); *2 denotes test drug group of lower dose;
  adjust (valuen / shift=0.1 adjustobs=(treat='3')); *3 denotes test drug group of higher dose;
run;
```

/*Part 3b, backup imputation method, for parameters with no missing data at baseline*/;

* Partial imputation to render monotone missing data;

```
proc sort data=ads;
  by treat1 treat2 strata1 strata2 ptid;
run;
```

```
proc mi data=ads out=monotone nimpute=2000 seed=97531;
  by treat1 treat2 strata1 strata2;
  var value;;
  mcmc chain=multiple impute=monotone;
run;
```

* Partial imputations to render monotone missing data; see Part 2a for dropping strata if not converge;

* To impute the missing data at post-baseline visits with penalty in test drug group ;

```
proc sort data= monotone;
  by _imputation_ ptid;
run;
```

```
proc mi data= monotone out=mi_1 nimpute=1 seed=75319;
  by _imputation_;
  class treat strata1 strata2;
  monotone reg ( / details);
  mnar model (value: / modelobs=(treat='1')); *1 denotes placebo group;
  mnar adjust (valuen / shift=0.1 adjustobs=(treat='2')); *2 denotes test drug group of lower dose;
  adjust (valuen / shift=0.1 adjustobs=(treat='3')); *3 denotes test drug group of higher dose;
  var strata1 strata2 value;;
```

run;

```
*****

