1 OVERVIEW AND INVESTIGATIONAL PLAN

1.1 STUDY DESIGN AND RANDOMIZATION

This is a Phase 3, multicenter and multinational, double-blind (single-blind Run-in Phase), placebo-controlled, parallel-group study. Patients were randomly assigned 1:1:1 to the following 3 treatment groups.

- Sotagliflozin 400 mg
- Sotagliflozin 200 mg
- Placebo

All patients will have a Screening Period comprised of an up to 2-week Screening Phase and a 2-week, single-blind placebo Run-in Phase prior to randomization. Following randomization, patients will have a 26-week, double-blind Treatment Period, 26-week, double-blind Extension Period, and a 4-week post-treatment Follow-up period (patients who prematurely discontinue the study treatment are expected to continue in the study).

At the end of the screening period, eligible patients will be centrally randomized (using permuted block randomization schedule) via an Interactive Response Technology (IRT).

The randomization will be stratified by:

- Hemoglobin A1c (HbA1c) at the screening ($\leq 8.5\%$ and $> 8.5\%$)
- Mean systolic blood pressure (SBP) at the screening visit (< 130 mmHg, ≥ 130 mmHg).

It is anticipated to randomize a total of approximately 276 patients.

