1.3 DETERMINATION OF SAMPLE SIZE

The sample size/power calculations were performed based on the primary endpoint. Assuming a common standard deviation of 1.2% and using a 2-sided test at a 0.05 α -level, 92 patients in each group will provide 80% power to detect a treatment difference of 0.5% in mean HbA1c change from Baseline to Week 26 between sotagliflozin 400 mg and placebo.

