Tipping point analysis based on the same multiple imputation method as applied to the primary analysis will be performed to examine the robustness of the results from the primary analysis. Patients who were randomized to sotagliflozin groups and had no HbA1c data at Week 26 will be given a penalty. The penalty will be gradually increased to evaluate at which level the conclusion of the analyses in terms of statistical significance is changed. The tipping point is the penalty level, at which the magnitude of efficacy reduction in patients without HbA1c data at Week 26 creates a shift in the treatment effect of sotagliflozin 400 mg from being statistically significantly better than placebo to a non-statistically significant effect. LS mean difference between sotagliflozin 400 mg and placebo and its associated p-value will be provided for each penalty level. The steps to perform the tipping point analysis comparing sotagliflozin 400 mg versus placebo are as follows:

1. Missing data will be imputed using the same MI method as applied to the primary analysis (see sample code Part 3 in Appendix A),
2. The imputed HbA1c value at Week 26 in the sotagliflozin 400 mg group will be penalized by adding a penalty δ (eg, $\delta = 0.1\%$) in each complete dataset (see sample code Part 3 in Appendix A),
3. Change from Baseline at Week 26 in HbA1c will be analyzed using the same ANCOVA model as specified in the primary analysis in each complete dataset (see sample code Part 4a in Appendix A),
4. Results will be combined across complete datasets using Rubin's rule (see sample code Part 5 in Appendix A),
5. Steps 2 to 4 will be repeated with incremental penalty at δ (ie, δ , 2δ , 3δ ,.....) until the p-value for treatment effect of sotagliflozin 400 mg compared to placebo estimated in Step 4 is > 0.05 .

The above tipping point analysis will be replicated to examine the robustness of the treatment effect of sotagliflozin 200 mg (ie, adding penalty to the sotagliflozin 200 mg group instead of sotagliflozin 400 mg group in Step 2).

The tipping point analysis will be performed on the ITT population. The tipping point analysis will be performed only if the corresponding primary or secondary variables (change from Baseline to Week 26 in HbA1c) is statistically significant at $\alpha = 0.05$ (2-sided).

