***** Part 4: ANCOVA *****
*****
```

```
proc mixed data=mi_2;
  by _imputation_;
  class treat strata1 strata2 country;
  model change= treat strata1 strata2 country value0;
  lsmeans treat /diff cl;
  lsestimate treat "A1 Placebo" 1 0 0 /cl;
  lsestimate treat "A2 200mg drug" 0 1 0 /cl;
  lsestimate treat "A3 400mg drug" 0 0 1 /cl;
  lsestimate treat "B1 200mg drug vs Placebo" -1 1 0 /cl;
  lsestimate treat "B2 400mg drug vs Placebo" -1 0 1 /cl;
  ods output LSMEstimates=LSMEstimates;
run;
```

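### The tipping-point sample code shifts both sotagliflozin arms, whereas the SAP steps that cite it penalise one arm at a time

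*SAP*

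**What the plan says.** SAP 2.4.4.1 (Sensitivity analyses) introduces the tipping-point analysis in general terms: "Patients who were randomized to sotagliflozin groups and had no HbA1c data at Week 26 will be given a penalty". The numbered steps are more specific. Step 2 reads "The imputed HbA1c value at Week 26 in the sotagliflozin 400 mg group will be penalized by adding a penalty", and Step 5 raises the penalty until 400 mg versus placebo is no longer significant at 0.05. A repeat for the lower dose is then described as "adding penalty to the sotagliflozin 200 mg group instead of sotagliflozin 400 mg group in Step 2". Steps 1 and 2 both name Appendix A Part 3 as their sample code.

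Part 3 has three penalised imputation blocks: retrieved dropouts and washout in Part 3a, and the back-up method in Part 3b. Each contains the line "mnar adjust (valuen / shift=0.1 adjustobs=(treat='2')); *2 denotes test drug group of lower dose", followed by a line with the same 0.1 shift for `treat='3'`, the 400 mg arm. No block shifts one arm alone.

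The imputed data sets then go to the Part 4 model, "model change= treat strata1 strata2 country value0". It is fitted to all three arms with no group-specific variance. The 400 mg contrast has weights -1, 0, 1, so the 200 mg arm has weight zero.

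**The concern.** The text and the code it cites define two different quantities. In the text, the 400 mg tipping point is the penalty on missing 400 mg patients that removes significance, with the 200 mg data left alone. In the code as intended, both arms are penalised together.

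The 200 mg arm has no weight in the 400 mg contrast, but it contributes to the shared residual variance. Moving part of that arm by a fixed amount widens its spread, raises the pooled variance and enlarges the standard error of 400 mg versus placebo. The reported 400 mg tipping point then depends partly on a penalty applied to an arm outside the comparison. The same holds in reverse for 200 mg.

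The SAP uses this analysis to examine the robustness of the primary result, and Section 1.6 names tipping-point analyses again for patients with PK anomalies. One programmer following the steps and another following the code could report different values under the same label.

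**Working it through.** **Inputs from the documents.** SAP 1.3: "Assuming a common standard deviation of 1.2% and using a 2-sided test at a 0.05" significance level, and "92 patients in each group will provide 80% power to detect a treatment difference of 0.5" percentage points. SAP 1.1: "Patients were randomly assigned 1:1:1 to the following 3 treatment groups". Appendix A Part 4: one residual variance, contrast -1, 0, 1.

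**Inputs assumed.** The documents give neither the share of patients with missing Week 26 HbA1c (m) nor the observed effect (d). I take m = 5% to 20%, equal across arms, and d = 0.4 to 0.8 points.

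**1. The plan's own figure.** n = 2 × (1.960 + 0.842)² × 1.2² / 0.5² = 90.4, so 91 per arm. At 92 per arm the standard error is 1.2 × √(2/92) = 0.177 and 0.5/0.177 = 2.83. Power is 0.807 (normal) or 0.803 (noncentral t). The 92 per group is reproduced. The SAP states no tipping-point value.

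**2. The estimate.** A penalty δ on a share m of the 400 mg arm cuts its advantage from d to d − mδ. A further shift of the 200 mg arm enters with weight zero, so the estimate is essentially the same in both versions.

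**3. The standard error.** A shift δ on a share m adds m(1−m)δ² to the variance within that arm. Over three equal arms the pooled variance is 1.2² + k·m(1−m)δ²/3, with k = 1 if one arm is shifted (text) and k = 2 if both are (code). At m = 10% the ratio of standard errors, code to text, within-imputation part only, is 1.0001 at δ = 0.1, √(1.50/1.47) = 1.010 at δ = 1, and 1.038 at δ = 2.

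**4. The tipping point.** Solve for δ:

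(d − mδ) / √{2[1.44 + k·m(1−m)δ²/3]/92 + 2m(1.44)/92} = 1.96

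The second term under the root approximates the between-imputation variance and is the same in both versions. Example with d = 0.5, m = 10%:

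- Text, δ = 1.30: pooled variance 1.44 + 0.09 × 1.69/3 = 1.491; standard error √[(2 × 1.491 + 0.288)/92] = 0.1885; 0.370/0.1885 = 1.96.
- Code, δ = 1.26: pooled variance 1.44 + 2 × 0.09 × 1.588/3 = 1.535; standard error √[(2 × 1.535 + 0.288)/92] = 0.1911; 0.374/0.1911 = 1.96 to rounding.

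Results in HbA1c percentage points (differences from unrounded values):

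| d | m | Text (400 mg only) | Code (both arms) | Lowering |
|---|---|---|---|---|
| 0.5 | 5% | 2.64 | 2.46 | 0.18 (7%) |
| 0.5 | 10% | 1.30 | 1.26 | 0.05 (4%) |
| 0.5 | 15% | 0.83 | 0.81 | 0.02 (2%) |
| 0.5 | 20% | 0.59 | 0.58 | 0.01 (2%) |
| 0.8 | 5% | 7.18 | 6.35 | 0.83 (12%) |
| 0.8 | 10% | 3.88 | 3.57 | 0.31 (8%) |
| 0.8 | 15% | 2.64 | 2.49 | 0.15 (6%) |
| 0.8 | 20% | 1.99 | 1.90 | 0.09 (4%) |

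At d = 0.4 the lowering runs from 0.02 (3%, m = 5%) to under 0.01 (0%, m = 20%).

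**5. Simulation check.** Three-arm ANCOVA with baseline, two strata and eight countries; residual SD 1.2; 200 mg effect 0.6 times the 400 mg effect; placebo-based washout imputation; 60 imputations combined by Rubin's rules; penalty raised in 0.1 steps. There were 150 trials per setting, and those significant at zero penalty were kept.

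| d | m | Median, text | Median, code | Median paired lowering | Trials with no lowering |
|---|---|---|---|---|---|
| 0.5 | 5% | 3.3 | 3.1 | 0.3 | 13% |
| 0.5 | 10% | 1.5 | 1.4 | 0.1 | 39% |
| 0.5 | 20% | 0.6 | 0.6 | 0.0 | 77% |
| 0.8 | 5% | 6.0 | 5.2 | 0.7 | 2% |
| 0.8 | 10% | 3.2 | 2.9 | 0.2 | 9% |
| 0.8 | 20% | 1.2 | 1.1 | 0.1 | 46% |

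The code's tipping point was higher than the text's in 0% to 4% of trials. Direction and order of size agree with step 4.

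**The case against.** The best defence is that Appendix A is labelled sample code and reads as a template. The shift is fixed at 0.1 with no loop, although Step 5 needs increments. A third stratification variable is sorted on but never defined. The subgroup example has two treatment groups in a three-arm trial. A programmer working from the numbered steps would penalise one arm. The introductory sentence, with its plural, can also be read as supporting the code.

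That limits the weight of the point but does not remove it. Steps 1 and 2 cite Part 3 as their implementation, no printed block carries out the one-arm penalty, and the wording of the 200 mg repeat leaves no doubt that one arm is meant.

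A second objection is that the printed program does not strictly shift both arms. A semicolon ends the MNAR statement after the `treat='2'` line and leaves the `treat='3'` line outside it. This is correct: the two-arm result is the evident intent, not the output of the text as printed. It makes repair more necessary. Anyone who tidied the code by dropping the stray line would penalise only the 200 mg arm, the wrong one for the primary comparison.

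Third, the tipping point is not the only robustness check. SAP 2.4.4.1 adds the control-based analysis when the retrieved-dropout method is primary, and Section 1.6 adds further imputation analyses. That stands.

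**Conclusion.** The conflict between the operative steps and the code they cite is real, and the introductory sentence is ambiguous. Following the code's intent usually gives a lower 400 mg tipping point than the one defined, by about 0% to 12% over the assumed ranges. At the planned effect of 0.5 with 10% or more missing, the calculated lowering is 0.05 or less; on a 0.1 grid the simulation shows a median of one step at 10% missing and none at 20%. The larger gaps arise with little missing data or a large effect, where the tipping penalty is already several HbA1c points. The error is conservative, and the primary estimate, confidence interval, p-value and testing hierarchy are untouched.

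A reader might infer more. One inference is that the code adds noise to the 400 mg comparison. It does not: the penalty is a fixed shift to imputed 200 mg values and acts mainly through the pooled variance. Another is that the tipping point falls by some set fraction. The documents give no missing share or observed effect, so only a range can be stated. A third is that the two doses' tipping points cannot be read separately under the code alone. The pooled variance links the arms to some degree under the text as well.

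The sizes assume equal missingness in each arm. The simulation uses placebo-based imputation only. Under the preferred method, discontinuers are imputed from retrieved dropouts in their own arm; the pooled-variance mechanism is the same there, but its size was not simulated.

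**What to change.** In both blocks of Part 3a and in Part 3b, write two separate runs. For the 400 mg tipping point, use a single complete statement, `mnar adjust (valuen / shift=... adjustobs=(treat='3'));`. For the 200 mg tipping point, use the same statement with `treat='2'`. In Part 3b, keep the adjustment together with the MNAR MODEL specification.

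Do not simply delete a line. The `treat='2'` line carries the `mnar` keyword, so removing it leaves the `treat='3'` line without a statement to belong to. Correct the comment in the first block of Part 3a that labels the higher dose as 2.

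In the introductory sentence of 2.4.4.1, replace the plural reference to the sotagliflozin groups with *the sotagliflozin group under test*. If a joint penalty on both arms is wanted, state it as a separate analysis.

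The cost is three rewritten code blocks, one extra run per penalty level and one edited sentence. No new data are needed and the primary analysis does not change.

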***** Part 4: ANCOVA *****
*****
```

```
proc mixed data=mi_2;
  by _imputation_;
  class treat strata1 strata2 country;
  model change= treat strata1 strata2 country value0;
  lsmeans treat /diff cl;
  lsestimate treat "A1 Placebo" 1 0 0 /cl;
  lsestimate treat "A2 200mg drug" 0 1 0 /cl;
  lsestimate treat "A3 400mg drug" 0 0 1 /cl;
  lsestimate treat "B1 200mg drug vs Placebo" -1 1 0 /cl;
  lsestimate treat "B2 400mg drug vs Placebo" -1 0 1 /cl;
  ods output LSMEstimates=LSMEstimates;
run;
```

*** Subgroup analyses using gender as an example;**

```
proc mixed data=mi_2;
  by _imputation_;
  class treat strata1 strata2 country gender;
  model change= strata1 strata2 country value0 treat*gender;
  lsmeans treat*gender /diff cl;
  lsestimate treat*gender "SA11 Placebo - Female" 1 0 0 0 /cl;
  lsestimate treat*gender "SA12 Placebo - Male" 0 1 0 0 /cl;
  lsestimate treat*gender "SA21 Test drug - Female" 0 0 1 0 /cl;
  lsestimate treat*gender "SA22 Test drug - Male" 0 0 0 1 /cl;
  lsestimate treat*gender "SB1 Test drug vs Placebo - Female" -1 0 1 0 /cl;
  lsestimate treat*gender "SB2 Test drug vs Placebo - Male" 0 -1 0 1 /cl;
  ods output Diffs=diffs Lsmestimates = Lsmestimates;
run;
```

```
*****

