### **Assessment of treatment effect by subgroup**

Descriptive analyses will be performed on the primary endpoint to summarize the treatment effects across subgroups defined by the following Baseline or Screening factors:

- Race
- Ethnicity (Hispanic, Not Hispanic)
- Age group (<50 years,  $\geq$ 50 to <65 years,  $\geq$ 65 years)
- Gender
- Baseline BMI level (<30,  $\geq$ 30 kg/m^2)
- Baseline HbA1c ( $\leq$ 8.5%, >8.5%)
- Baseline SBP (<130 mmHg,  $\geq$ 130 mmHg)
- Country.

The treatment effects across the subgroups defined for each of these factors will be estimated for the change from baseline to Week 26 in HbA1c in the ITT population, and using a similar approach to the analysis for the primary efficacy endpoint. The adjusted estimates of treatment mean differences (comparing sotagliflozin 400 mg versus placebo) with SE and 95% CIs will be provided as appropriate across the subgroups using contrast statements.

In the event that the subgroup factor is identical or similar to a randomization strata factor (eg, baseline HbA1c category); only the subgroup factor (as a single factor and/or an interaction term) will be included in the model in order to avoid the issue of collinearity in the analysis. The corresponding strata factor will not be included in the model.

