If the retrieved dropout imputation is applied to the primary analysis, the analysis based on the control-based imputation (ie, the backup imputation method) will be presented as a sensitivity analysis.

Assessment of treatment effect by subgroup

Descriptive analyses will be performed on the primary endpoint to summarize the treatment effects across subgroups defined by the following Baseline or Screening factors:

- Race (White, Black or African American, Asian, Other) (any race groups with fewer than 5 patients may be combined with “Other” category as appropriate),
- Ethnicity (Hispanic, Not Hispanic),
- Age group (<50, ≥ 50 to <65, ≥ 65 years) (any category with fewer than 5 patients may be combined with another category as appropriate),
- Gender (Male, Female),
- Baseline BMI level (<30, ≥ 30 kg/m²),
- Baseline HbA1c ($\leq 8.5\%$, $> 8.5\%$),
- Baseline mean SBP (<130 mmHg, ≥ 130 mmHg),
- Duration of diabetes (<10, ≥ 10 years),
- Prior antidiabetic medication (insulin, non-insulin),
- Country.

The treatment effect (sotagliflozin 400 mg versus placebo) across the subgroups defined for each of these factors will be estimated for the change from Baseline to Week 26 in HbA1c in the ITT population, and using the same MI method as applied to the primary analysis as applied to the analysis for the primary efficacy endpoint. The ANCOVA model will include treatment groups (sotagliflozin 400 mg, sotagliflozin 200 mg, placebo), randomization stratum of HbA1c ($\leq 8.5\%$, $> 8.5\%$), randomization stratum of SBP (<130, ≥ 130 mmHg), subgroup factor, treatment-by-subgroup factor, and country as fixed factors and using baseline HbA1c value as a covariate. The adjusted estimates of treatment mean differences (sotagliflozin 400 mg versus placebo) with standard error (SE) and 95% CIs will be provided as appropriate across the subgroups (see sample code Part 4a in [Appendix A](#)). A graphical presentation of the results (ie, forest plot) will also be provided.

Similarly, the treatment effect across the subgroups will be estimated for the comparison of sotagliflozin 200 mg versus placebo as a sensitivity analysis.

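### The sample subgroup code gives four contrast coefficients for a six-cell factor, so no labelled row estimates the planned 400 mg versus placebo comparison

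*SAP*

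**What the plan says.** The governing text is clear. SAP section 2.4.4.1, under the subgroup heading, states: "The treatment effect (sotagliflozin 400 mg versus placebo) across the subgroups defined for each of these factors will be estimated". The model keeps all three arms: "The ANCOVA model will include treatment groups (sotagliflozin 400 mg, sotagliflozin 200 mg, placebo", with the subgroup factor and its interaction with treatment added. The lower dose has a secondary role: "the treatment effect across the subgroups will be estimated for the comparison of sotagliflozin 200 mg versus placebo as a sensitivity analysis". Protocol section 11.4.2.1 agrees on the dose to be reported: "The adjusted estimates of treatment mean differences (comparing sotagliflozin 400 mg versus placebo) with SE and 95% CIs".

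The same SAP section refers the analyst to Part 4a of Appendix A. No block carries that label; the only subgroup code stands in Part 4, directly below the main ANCOVA. The main ANCOVA names each dose in its contrasts, for example "B2 400mg drug vs Placebo" with coefficients `-1 0 1`. The subgroup block, which takes gender as its example, names no dose. It uses one generic test-drug label and four coefficients per row, as in "SB1 Test drug vs Placebo - Female" with `-1 0 1 0`.

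**The concern.** The subgroup contrasts are laid out for two arms, but the model has three. The position where the code puts the test drug is the position the rest of the appendix gives to 200 mg. The row label does not name the dose, so a reader of the output would not see the substitution. What is at stake is the descriptive subgroup table and forest plot for the primary comparison: they could show the dose that the SAP assigns to a sensitivity analysis, presented as if it were the main comparison.

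**Working it through.** The plan states no figure to reproduce here. The check is a count of cells and a reading of coefficient positions.

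**Inputs**
- Treatment levels: 3 (SAP 2.4.4.1). Gender levels: 2, "Gender (Male, Female" (same section).
- Treatment coding: the tipping-point code in Appendix A, Part 3 treats 1 as placebo, 2 as the lower dose and 3 as the higher dose. (One comment there prints 2 beside the statement for level 3; the other comments and the statements themselves are consistent.) The main ANCOVA in Part 4 uses the same order: 200 mg is `0 1 0` and 400 mg is `0 0 1`.
- Data: the subgroup block reads `mi_2`, the data set name used by the three-arm main ANCOVA, and shows no restriction to two arms.
- Cell order: the CLASS statement lists treatment before gender, so gender varies fastest. The code's own labels put Female before Male.

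**Count.** 3 × 2 = 6 cells. Four coefficients match only a 2 × 2 = 4 layout.

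**Positions**

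| Position | 1 | 2 | 3 | 4 | 5 | 6 |
|---|---|---|---|---|---|---|
| Cell | placebo F | placebo M | 200 mg F | 200 mg M | 400 mg F | 400 mg M |
| SA21 | 0 | 0 | 1 | 0 | – | – |
| SA22 | 0 | 0 | 0 | 1 | – | – |
| SB1 | -1 | 0 | 1 | 0 | – | – |
| SB2 | 0 | -1 | 0 | 1 | – | – |

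SA21 and SA22 are the 200 mg cell means. SB1 and SB2 are 200 mg minus placebo in females and in males. Positions 5 and 6, the 400 mg cells, receive nothing.

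**Other cell order.** If gender varied slowest, SB1 would happen to be 400 mg minus placebo in females, but SB2 would be placebo males minus 200 mg females. That order does not rescue the block.

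**Numerical check.** Three-arm data were simulated with assumed effects of -0.20 (200 mg) and -0.50 (400 mg) and residual SD 1.2, and fitted with the same cell-means model without country. Omitted trailing coefficients were set to zero.

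| Contrast | Female | Male |
|---|---|---|
| As printed (four coefficients) | -0.200 | -0.197 |
| Six coefficients, 400 mg vs placebo | -0.507 | -0.504 |

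The printed contrasts return the assumed 200 mg effect; the six-coefficient contrasts return the 400 mg effect.

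**What is pooled.** The block also requests all pairwise differences of the treatment-by-gender means and saves them in `diffs`, so the 400 mg differences exist for each imputed data set. Part 5, however, applies Rubin's formula only to `Lsmestimates`, the labelled rows.

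The sample model omits the separate treatment and gender main effects. That is not an error, because the interaction term alone spans the same six cell means.

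**The case against.** The strongest reply is that this is sample code under correct text. The block is offered as an example and looks like a template: a single generic test drug, a 2 × 2 layout and, elsewhere in the appendix, a stray third stratum in a trial with two. It cannot be used unchanged for race, age or country, so a programmer must adapt it, and the correct dose-labelled contrasts stand directly above it. The 400 mg differences are in the saved pairwise output. The analysis is descriptive and outside the testing hierarchy in SAP section 2.4.4.4.

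All of that stands and limits the weight of the point. It does not make the block right. The SAP cites Appendix A for this analysis, the labelled rows are the only ones Part 5 pools, and none of them is the planned comparison.

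Two stronger readings are tempting. A reader might infer that the trial will report the wrong dose. The documents do not support this: it needs the code to be used unadapted and the software to fill omitted coefficients with zero, and the documents establish neither.

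A reader might also infer that the reported effects would be about half the true ones. Protocol section 4.3 gives Phase 2b HbA1c reductions of 0.52% (200 mg), 0.93% (400 mg) and 0.14% (placebo), so 0.52 - 0.14 = 0.38, 0.93 - 0.14 = 0.79 and 0.38/0.79 = 0.48. Those are 12-week results from a study not described as enrolling CKD stage 4 patients. Protocol section 4.1 explains that the renal part of the effect falls with filtration rate. The ratio is an illustration, not an estimate for this trial.

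**Conclusion.** The point holds as a defect in the sample code, not in the planned comparison. It is certain that four coefficients do not fit a six-cell factor and that, in the appendix's own order, the labelled Test drug rows do not estimate 400 mg versus placebo. It is conditional that wrong-dose results would appear: if omitted trailing coefficients are taken as zero, the pooled rows and the forest plot drawn from them would show 200 mg versus placebo with no dose named. If they are not, the statements do not run as intended. On neither reading do these rows give the planned comparison.

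The size of any numerical error cannot be fixed from the documents, because they state no expected 200 mg effect in this population. Taking the 0.5% difference from Protocol section 11.1 for 400 mg, and assuming a 200 mg effect anywhere from 0 to 0.5%, the error in each subgroup estimate would run from 0.5 - 0 = 0.5 percentage points down to 0.5 - 0.5 = 0. The primary analysis is unaffected, since its contrasts in Part 4 are correct. This is a modest correction that should be made.

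**What to change.** Replace the four-coefficient rows in Appendix A, Part 4 with six-coefficient rows that name the dose, in the order placebo F, placebo M, 200 mg F, 200 mg M, 400 mg F, 400 mg M:

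- 400 mg vs placebo, Female: `-1 0 0 0 1 0`
- 400 mg vs placebo, Male: `0 -1 0 0 0 1`
- 400 mg mean, Female: `0 0 0 0 1 0`; Male: `0 0 0 0 0 1`
- 200 mg vs placebo (sensitivity), Female: `-1 0 1 0 0 0`; Male: `0 -1 0 1 0 0`

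State the general rule for a factor with k levels. There are 3k cells; for level j put -1 in position j, and +1 in position 2k + j for 400 mg or k + j for 200 mg. The three age groups, for example, need 3 × 3 = 9 coefficients, and the first age group for 400 mg is `-1 0 0 0 0 0 1 0 0`.

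Correct the Part 4a reference so that it leads to this block. SAP section 1.6 says the first step analysis has already been run for top line results, so check any subgroup output already produced against the corrected contrasts. The cost is a few lines of code and one comparison of outputs; no change to the design, the data or the primary analysis is needed.
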